4.3 Randomisation and number of subjects

Twelve (12) eligible and consenting subjects will be included in one (1) of two (2) dose groups, six (6) subjects in each dose group.

This is a non-randomised trial. Trial will include one pre-defined starting dose [REDACTED] and one ascending dose level [REDACTED].

4.4 Subject replacement

The trial subjects withdrawn for medical/safety reasons will not be replaced.

Withdrawals due to non-medical/safety reasons including voluntary withdrawals can be replaced if subjects are not evaluable. See CTP for additional details.

4.5 Blinding

This is an open-label trial, and the allocation of treatments will not be blinded.

5 STATISTICAL AND ANALYTICAL PLANS

5.1 Statistical hypotheses

One of the trials endpoints is to investigate if the pharmacokinetic AUC and C_{max} are proportional to the dose administered. Please refer to section 9.1.1.1 below for more details about the dose proportionality analyses.

5.2 Sample size calculation

No formal sample size calculation has been performed for this trial. The size of the dose groups is considered sufficient to provide adequate information on the safety and PK parameters for the purpose of this trial.

5.3 Definition of analysis sets

The analysis sets defined for the trial are outlined in Table 2.

Table 2 Analysis sets

| Analysis set | Definition | Use of analysis set |
|-------------------------------------|--|---|
| Full analysis set (FAS) | All subjects who have received treatment with investigational medicinal product (IMP) | The FAS will be used for safety and tolerability assessments and description of trial population. |
| Pharmacokinetic analysis set (PKAS) | All subjects who received IMP, who provided an evaluable plasma concentration profile and who have no AEs or protocol deviations judged to affect the PK analysis. Individual PK values may be excluded from the analysis. | PK endpoints. |

5.4 Definition of baseline

Baseline is defined as the latest measurement prior to IMP exposure.

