- Vital signs (blood pressure, heart rate and body temperature)
- Safety laboratory measurements

Exploratory endpoints:

- Metabolite profile in plasma
- Profile of excreted metabolites in urine

Number of subjects planned

12 healthy subjects will be included in two dose groups.

Diagnosis and main eligibility criteria

Healthy elderly volunteers ≥ 65 and < 90 years of age, with a weight of 50 to 110 kg, who are willing to comply with trial procedures and who have given written consent, will be considered eligible for participation in the trial.

Methodology

Twelve (12) eligible and consenting subjects will be allocated to two dose groups. All subjects will be assigned to a single dose treatment with IRL757, 6 subjects to dose 1 and 6 subjects to dose 2.

Eligible subjects will be confined to the research clinic from the evening before first dosing (Day -1) until 48 hours following dosing. The subjects should be fasting overnight (10 hours) before dose administration on Day 1. A Follow-up Visit will be performed 5-10 days after administration of IMP.

Investigational Medicinal Products (IMP), dosage and mode of administration

IRL757 half-life is expected to be 4-10 hours.

IRL757 capsules**Duration of treatment**

Subjects included in the study will receive one dose of IRL757.

Duration of each subject's involvement in the trial

Subjects will be screened for eligibility according to trial-specific inclusion/exclusion criteria at Visit 1 (Screening visit) within 28 days prior to IMP administration.

A Follow-up Visit will be performed for all subjects 5-10 days after last administration of IMP.

Statistical methods

No formal sample size calculation has been performed for this trial. The size of the dose group is considered sufficient to provide adequate information on the safety and PK parameters for the purpose of this trial.

All statistical calculations will be performed using the SAS® version 9.4 or later (SAS Institute Inc., Cary, NC, USA). The statistical analyses will only include descriptive statistics reflecting the explorative nature of the trial. In general, the data will be presented by dose group.

Continuous data will be summarised by dose group using number of observations, mean, standard deviation (SD), median, minimum and maximum. Categorical data will be summarised by dose group using the number and percentage of subjects in each category.

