Time /assessment	Admission	Pre-dose	0	20min	30min	40min	1 h	2 h	3 h	4 h	6 h	8 h	10h	12 h	24 h	48 h
Inclusion/exclusion criteria		X														
Physical examination		X														X ¹
C-SSRS																X
Blood pressure, heart rate, respiratory rate	X	X			X		X	X		X		X		X	X	X
Body temperature	X															X X
Haematology, clinical chemistry, coagulation	X															X
Urinalysis	X															
Drugs of abuse	X															
Alcohol screen	X															
ECG	X ²	X ³					X	X	X		X			X	X	X
IMP administration			X													
Blood sampling ^{4, 6} (PK and metabolite pattern analysis)		X		X		X	X	X	X	X	X	X	X	X	X	X
PK urine sampling ⁵		X														
Baseline symptoms	X	X														
AE reporting									X							X
Concomitant medications	X	X							X							X

¹ Symptom-driven physical examination.

² Triplicate ECGs separated by at least 1 min at Day -1.

³ Within 60 min prior to dose at Pre-dose.

⁴ Within 60 min pre-dose and 20 (±2) min, 40 (±4) min, 1 hour (±6 min), 2 hours (±12 min), 3 hours (±18 min), 4 hours (±24 min), 6 hours (±30 min), 8 hours (±30 min), 10 hours (±30 min), 12 hours (±30 min), 24 hours (±1 hour) and 48 hours (±1 hour) post-dose.

⁵ Urine collection in fractions 0-6, 6-12, 12-24, 24-36 and 36-48 h post-dose. Subjects to empty their bladder prior to dose for urine collection (a pre-dose sample will be retained). A sample of approx. 2 mL from each fraction will also be kept and divided into 2 aliquots for metabolite pattern analysis.

⁶ Plasma obtained at each time point will be divided into two samples, one for PK analysis and one for metabolite pattern analysis. Each of these samples will be separated into two aliquots.

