9 STATISTICAL METHODOLOGY

In general, data will be presented in tables with the number of observations, arithmetic mean, standard deviation (SD), median, minimum and maximum value for continuous data. In addition, 95% confidence intervals (CIs) will be added for ECG, vital signs and safety laboratory data. Categorical data will be presented with counts and percentages. All collected data will be listed by subject and dose group, except for data pertaining to the exploratory endpoints which will be reported elsewhere. Data is generally presented by dose group.

Details on statistical analyses and descriptive summaries are specified below.

All statistical analyses and descriptive summaries will be performed using SAS version 9.4 (SAS institute, Cary, NC).

PK parameters will be calculated by Non-Compartmental Analysis (NCA) using the software Phoenix WinNonlin® version 8.3 (Certara, U.S.A).

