9.2 Analysis of secondary endpoints

9.2.1 Adverse Events (AEs)

AEs and serious AEs (SAEs) will be recorded from the time when informed consent is obtained until the Follow-up Visit. AEs that occur before first treatment with IMP (baseline symptoms) will be listed separately.

All AEs will be described in terms of the dose at which they occurred. AEs will be summarised by System Organ Class (SOC) and Preferred Term (PT) using the Medical Dictionary for Regulatory Activities (MedDRA) vocabulary. The number of subjects reporting AEs, and the number of AEs reported will be presented. The events will be tabulated by SOC, PT and by severity and relationship to IMP. SAEs will be presented in the same tabulations.

9.2.2 *Physical examinations*

Normal and abnormal findings will be specified and summarised by dose group.

9.2.3 *Electrocardiogram (ECG)*

All continuous ECG data will be listed for each subject and summarised by dose group. In addition, ECGs will be categorised as "normal", "abnormal, not clinically significant", or "abnormal, clinically significant" (as judged by the Investigator) and summarised by dose group.

9.2.4 *Vital signs*

Vital signs (blood pressure, heart rate, respiratory rate and body temperature) will be summarised by dose group.

9.2.5 *Safety laboratory analyses*

Safety laboratory data will be summarised by dose group. Safety laboratory interpretations will be summarised by dose groups using frequency tables.

9.2.6 *Columbia-Suicide Severity Rating Scale (C-SSRS)*

This rating scale will be administered for screening of suicidal ideation and behaviour throughout the trial. No formal statistical analysis of the outcome will be performed, i.e., the data will be listed only. Any abnormal findings will be listed and treated as AEs or SAEs.

9.3 *Analysis of exploratory endpoints*

The analysis and results pertaining to the exploratory endpoints, plasma and urine metabolite profiles, will be detailed in a separate report, and hence are not covered in this SAP.

9.4 *Description of trial population*

9.4.1 *Disposition*

A subject disposition will be presented showing the number of screened subjects; the number of withdrawn subjects prior to dose, including the reason for withdrawal; the number of included subjects in each dose group; the number of withdrawn subjects, including the reason for withdrawal; the number of completed subjects; the number of subjects included in the analysis sets, and the number of subjects at each visit.

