| [PARAMETER 1] (unit) | Measured value | [Assessment timepoint 1] | n Mean (SD) Median (Min, Max) 95% CI (lower, upper) | xx x.xx (x.xx) x.xx (x.x, x.x) (x.xxxx, x.xxxx) |
| | | [Assessment timepoint 2] | n Mean (SD) Median (Min, Max) 95% CI (lower, upper) | xx x.xx (x.xx) x.xx (x.x, x.x) (x.xxxx, x.xxxx) |
| Change from baseline | | [Assessment timepoint 2] | n Mean (SD) Median (Min, Max) 95% CI (lower, upper) | xx x.xx (x.xx) x.xx (x.x, x.x) (x.xxxx, x.xxxx) |
| Relative change from baseline (%) | | [Assessment timepoint 2] | n Mean (SD) Median (Min, Max) 95% CI (lower, upper) | xx x.xx (x.xx) x.xx (x.x, x.x) (x.xxxx, x.xxxx) |

Data based on [population]. CI: Confidence interval. n: Number of observations. SD: Standard deviation. NC: Not calculated - number of evaluable observations less than 3. NA: Not available - no evaluable observations. SAS program: [PROGRAM NAME].sas.

Dataset version: ADXX YYYY-MM-DDTHH:MM:SS. Run by: [USERNAME] YYYY-MM-DDTHH:MM:SS. EDC data extracted: YYYY-MM-DDTHH:MM:SS.

Table EG 2 ECG interpretations (Full analysis set)

| Assessment | Assessment timepoint | | IRL757 [REDACTED] (N=6) | IRL757 [REDACTED] (N=6) |
|---------------|--------------------------|------------|-------------------------------|-------------------------------|
| [PARAMETER 1] | [Assessment timepoint 1] | [RESULT 1] | xx/XX (xx%) | xx/XX (xx%) |
| | | [RESULT 2] | xx/XX (xx%) | xx/XX (xx%) |
| | | [RESULT 3] | xx/XX (xx%) | xx/XX (xx%) |
| | [Assessment timepoint 2] | [RESULT 1] | xx/XX (xx%) | xx/XX (xx%) |
| | | [RESULT 2] | xx/XX (xx%) | xx/XX (xx%) |
| | | [RESULT 3] | xx/XX (xx%) | xx/XX (xx%) |

Data based on [population]. SAS program: [PROGRAM NAME].sas.

Dataset version: ADXX YYYY-MM-DDTHH:MM:SS. Run by: [USERNAME] YYYY-MM-DDTHH:MM:SS. EDC data extracted: YYYY-MM-DDTHH:MM:SS.

10.2.3.4 *Vital signs*
Table VS 1 Vital signs measurements (Full analysis set)

| Assessment (unit) | Result category | Assessment timepoint | IRL757 [REDACTED] (N=6) | IRL757 [REDACTED] (N=6) |
|-----------------------------------|-----------------|--------------------------|--|--|
| [PARAMETER 1] (unit) | Measured value | [Assessment timepoint 1] | n Mean (SD) Median (Min, Max) 95% CI (lower, upper) | xx x.xx (x.xx) x.xx (x.x, x.x) (x.xxxx, x.xxxx) |
| | | [Assessment timepoint 2] | n Mean (SD) Median (Min, Max) 95% CI (lower, upper) | xx x.xx (x.xx) x.xx (x.x, x.x) (x.xxxx, x.xxxx) |

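### Does taking the pre-dose ECG as baseline, and leaving out the Day -1 triplicate, make the ECG change-from-baseline intervals needlessly wide?

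*SAP*

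**What the plan says.** SAP section 5.4 defines baseline once, with no exception for ECG: "Baseline is defined as the latest measurement prior to IMP exposure".

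The protocol's Table 2 schedules two ECG sessions in the clinic before dosing. Footnote 2 covers admission: "Triplicate ECGs separated by at least 1 min at Day -1". Footnote 3 covers Day 1: "Within 60 min prior to dose at Pre-dose". Only the Day -1 entry carries the triplicate footnote, so the pre-dose ECG is single by inference; no text gives its number. Subjects are "confined to the research clinic from the evening before first dosing (Day -1", so the triplicate is an evening recording, while the pre-dose tracing follows an overnight fast.

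SAP section 9 states that "95% confidence intervals (CIs) will be added for ECG, vital signs and safety laboratory data". Table EG 1 of the SAP shows measured values, "Change from baseline" and relative change, each with such an interval, by dose group. Section 4.3 gives "six (6) subjects in each dose group". Section 9.2.3 adds: "All continuous ECG data will be listed for each subject and summarised by dose group". The triplicate therefore stays in the listings and is not excluded from the measured-value rows. It only does not enter the baseline.

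**The concern.** Four pre-dose tracings are collected in the clinic, and the rule appears to use one. Noise in that tracing enters every change value of that subject, from 1 h to follow-up. In a group of six, a chance high or low baseline could move the whole change profile, and there is no placebo group to expose it. ECG is a secondary safety endpoint, so a noisier baseline could hide or mimic a shift in an interval or in heart rate. An obvious alternative is to average the Day -1 triplicate mean with the Day 1 pre-dose value, which needs no new data. If that reliably narrowed the intervals, the plan would be giving up free precision. Read literally, the rule would also take the third replicate alone if the pre-dose tracing were missing.

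**Working it through.** The plan states no ECG standard deviation or interval width, so there is no figure to reproduce. What can be checked is whether averaging the two sessions narrows the intervals.

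**Inputs from the documents.** Six subjects per group; three ECGs on Day -1; one ECG pre-dose (inferred); post-dose ECGs at 1, 2, 3, 6, 12, 24 and 48 h and at follow-up; 95% intervals. **Assumptions.** s² is the variance of a single tracing within a day. A between-day variance ρs² is shared by all tracings of one subject on one day. The documents give neither s nor ρ.

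**Planned interval.** Half-width = t(0.975, 5 df)/√6 × SD(change) = 2.571/2.449 × SD(change) = 1.049 × SD(change). On Day 1 the day effect cancels between the pre-dose and post-dose tracings. Hence Var(change) = 2s² and the half-width is 1.049 × 1.414 s = 1.48 s.

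**Where 13% to 18% comes from.** Split s² into a session part S and a replicate part R, with no day effect. The planned variance is 2S + 2R. With the two sessions averaged it is (S + R) + (S + R)/4 + (S + R/3)/4 = 1.5S + 1.333R. The width ratio is √0.75 = 0.866 if R = 0 and √0.667 = 0.816 if S = 0. The algebra is right, but the model treats Day 1 pre-dose and Day 1 post-dose tracings as no more alike than Day -1 and Day 1 tracings.

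**Adding the day effect, Day 1 times (1, 2, 3, 6, 12 h).** Averaging leaves ½(Day 1 effect − Day -1 effect) in the change, which adds 2ρs²/4 = 0.5ρs². With all within-day variance at replicate level, the case kindest to averaging, Var(change) = s²(1.333 + 0.5ρ), against 2s² as planned:

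| ρ | Variance, averaged (s²) | Width relative to plan |
|---|---|---|
| 0 | 1.333 | 0.82 |
| 1/3 | 1.500 | 0.87 |
| 2/3 | 1.667 | 0.91 |
| 1 | 1.833 | 0.96 |
| 4/3 | 2.000 | 1.00 |
| 2 | 2.333 | 1.08 |

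Break-even is 0.5ρ = 0.667, so ρ = 4/3. If all within-day variance is at session level, it is 0.5ρ = 0.5, so ρ = 1. The range of 13% to 18% is therefore no bound for these five times.

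**24 h, 48 h and follow-up.** These fall on other days, so nothing cancels. With independent day effects the variance is s²(2 + 2ρ) as planned and s²(1.333 + 1.5ρ) averaged. The reduction lies between 25% and 33% for every ρ.

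**Equivalent sample size.** Variance ratios of 0.75 and 0.667 give 6/0.75 = 8 and 6/0.667 = 9 subjects. That does not carry over to interval width, because the interval keeps 5 df. Relative to n = 6, the t-based width is 0.881 at n = 7 and 0.797 at n = 8, so 0.866 and 0.816 both correspond to between 7 and 8 subjects.

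**Bias.** If the evening recording differs systematically from the pre-dose one by δ, averaging shifts every change by δ/2. In the best case, ρ = 0, averaging reduces the variance of the group mean change by (2 − 1.333)s²/6 = 0.111s². The squared bias δ²/4 exceeds this once δ > √0.444 s = 0.67 s. For an assumed s of 8 ms that is about 5.3 ms. With ρ above 0, a smaller offset suffices on Day 1.

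**The case for a change.** The strongest case for the concern is that equal weighting of the two sessions is fairly robust. It still narrows the Day 1 intervals by about 4% at ρ = 1, where taking the mean of all four tracings widens them by 9% and using the triplicate alone widens them by 29%. At 24 h, 48 h and follow-up it gains at any ρ under the model above. The change from the pre-dose value could be kept as a supporting display to guard against a time-of-day offset. The SAP never mentions the triplicate. It does not say whether the three values are averaged, and Table EG 1 counts observations, so a literal Day -1 row could show 18 values from six subjects. The rule also does not foresee a missing pre-dose tracing.

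The variance arithmetic stands as conditional statements. It does not show that the planned intervals are wider than the data allow, because that depends on a ρ nobody has stated. Nor does it answer the bias: the supporting display would simply be the present plan, and the lack of a placebo group counts against the averaged baseline as much as against the planned one. The silence on the triplicate is real. It is a missing detail that an analyst would settle by averaging replicates to one value per subject, and the public protocol is a synopsis, so the full protocol may already cover it.

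**Conclusion.** The rule in SAP section 5.4 gives a usable ECG baseline: a recording within an hour of dosing, on the same day and under the same conditions as most of the post-dose tracings. The documents do not establish a loss of precision from leaving out the triplicate. At the five Day 1 times, averaging the two sessions could narrow the intervals by up to 18%, change nothing or widen them; at the three later times a narrowing of 13% to 18% is plausible. Both statements rest on an assumed variance model and on the pre-dose ECG being single. Against any gain stands a possible time-of-day bias that a narrower interval would not show. Reasonable statisticians could choose either baseline. No test, threshold or decision rule depends on the ECG summaries, and no figure in the plan comes out wrong. What remains is optional clarification of how the triplicate is summarised and what serves as baseline if the pre-dose tracing is missing.

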5.5 Rounding principles

Generally, no rounding of data will be done prior to calculating statistics. However, if reported data contains more than 8 significant digits it will be rounded to 8 significant digits in the database.

In statistical output and descriptive summaries, the following principles will be used:

- Data will be presented as reported in input data in listings.
- Two (2) significant digits will be used for percentages (for example relative change from baseline).
- p-values and similar statistical output will be presented using 4 decimal places.
- Three (3) significant digits will be used for PK parameters when presenting min and max values in tables.
- Descriptive summaries (e.g., mean, SD, median etc.) of PK parameters will be presented with 4 significant digits.
- Descriptive summaries (e.g., mean, SD, median etc.) of all other numerical data will be presented with one extra decimal compared to reported input data.

5.6 Significance level

All statistical hypotheses in this trial will be answered using two-sided 90% confidence intervals.

5.7 Handling of dropouts, missing data and outliers

Outliers will be included in summary tables and listings and will not be handled separately in any analyses. All collected data, even if not tabulated, will be listed. Generally, no imputation of data will be performed. However, when calculating statistics for PK plasma concentrations, concentrations under LLOQ will be replaced with LLOQ/2 if more than 50% of the values for a given time point are above LLOQ. For figures presenting individual PK concentrations, no imputation is performed for values under LLOQ. For imputation of PK plasma concentration below LLOQ with the purpose of calculating PK parameters, see Section 9.1.1.

Safety laboratory concentrations under LLOQ will be replaced with LLOQ/2 and concentrations over ULOQ will be replaced with ULOQ for the purpose of calculating descriptive statistics.

In case of missing start and stop times of AEs that cannot be investigated further, missing data will be imputed according to a worst-case scenario, i.e., start time will be imputed as the closest time point post first intake of IMP and end time as 23:59, resulting in the longest possible treatment emergent duration of the AE.

6 CHANGES FROM THE CLINICAL TRIAL PROTOCOL

Changes to the planned analyses and the timing of these are summarised in Table 3.

Table 3 Changes in the planned statistical analyses

| Change category | Timing of change | Description of change | Reason for change |
|--|------------------|--|--|
| Change in the SAP compared to the protocol | Prior to DBL | Added frequency tables for safety laboratory interpretations | To provide a better overview of the safety laboratory data. |
| Change in the SAP compared to the protocol | Prior to DBL | Removed dose proportionality for metabolite M1 | Not relevant with dose proportionality for M1 due to [REDACTED] polymorphism |

7 CLINICAL DATABASE PROCESSING

7.1 General information

The clinical database is processed and generated according to The Clinical Data Interchange Standards Consortium (CDISC). CDISC is a Standard Developing Organization which develops and publishes standards to normalise the structure of clinical trial data and thereby simplify submissions to and reviews by authorities such as the Food and Drug Administration (FDA).

The CDISC standards for clinical studies are the Trial Data Tabulation Model (SDTM) and the Analysis Data Model (ADaM). The trial data will be structured into a database model reflecting the SDTM and will be compliant to SDTM Implementation Guide (SDTM-IG) version 3.3. The data used for statistical analysis will be structured to reflect the ADaM and be compliant to ADaM Implementation Guide (ADaM-IG) version 1.3.

Data values are collected according to, or mapped into, controlled terminology codelists defined by CDISC, whenever possible. The codelists are updated quarterly at CTC and the latest version available at trial start will be used. As per default, controlled terminology codelists will be used in all tables, listings, and figures. Custom codelists for test or parameter names will be used if applicable upon Sponsor's request, to align with protocol texts, or to adhere to other standard naming conventions (e.g., PK parameter name "Tmax" will be used instead of the CDISC term "Time of CMAX"). These custom codelists will be mapped in the "Parameter Name" field in the ADaM structure, while the CT will be kept in the SDTM predecessor fields to provide traceability back to CDISC codelists.

